# Data and Safety Monitoring Plan.

PI will be responsible for monitoring data and safety of all study participants. The Boston University IRB will oversee the process. The risks of this project are small, and the likelihood of significant adverse events is low. The following steps will be implemented to ensure data is secure:

- Web Form/Data Security. Information posted on forms will be electronically encrypted secure socket layering (SSL) encryption technology so that only the intended recipient can decode the data. Files stored on BUMC servers will be protected by electronic 'firewalls' that restrict access to designated users. This system utilizes unique login names and passwords and identifies the IP address of the user's computer. Data is stored on a secure server to which only designated individuals have access.
- **Database Infrastructure**. Access to the database will be implemented by means of unique login names and passwords. Data will be stored on a secure server to which only designated individuals have access. Database is backed up on a nightly basis.
- **Database Security**. Database security provided by BUMC OIT. Because the server will be part of the BUMC network NT domain, only connections from users authenticated from the domain controller are accepted, thus providing a secure environment for all Center data. The policy for computer systems security implemented at BUMC: (1) Provide physical security of data; and (2) Provide virtual security via connectivity.
- **Provide Security for Data**. All data are protected with disaster recovery via several methods: (1) Hardware redundancy; (2) Data backup, and (3) Data Security.

## 11 Statistical Plan

## 11.1 Study Aims

**Aim 1.** To adapt our previously developed patient navigation primary care-based smoking cessation intervention into a scalable intervention delivered to recently hospitalized smokers at a large urban safety- net hospital. **Aim 2.** To determine the acceptability and feasibility of the adapted patient navigation hospital-based smoking cessation intervention by pilot testing it among 25 smokers at a large urban safety-net hospital.

# 11.2 Sample Size Determination

The aim of this study is to determine the acceptability and feasibility of an adapted patient navigation smoking cessation intervention by pilot-testing it among 25 smokers at a large urban safety-net hospital. We will conduct a pilot RCT,

randomizing fifty hospitalized smokers to one of 2 study arms. We believe an n of 50 is the necessary sample size to determine acceptability and feasibility, and to have publishable results.

#### 11.3 Statistical Methods

For categorical outcomes of engagement and self-report cessation, we plan to report percentages and 95% confidence intervals; for continuous outcomes we examine means, standard deviations, and ranges. In order to determine if the patient navigation condition achieves greater smoking cessation at 3-month follow-up compared to standardized inpatient counseling condition, we will compare groups using chi- square tests and note differences that are statistically significant at the  $\alpha$ < 0.05 level. Analyses will be based on intent-to-treat.

We will use multiple logistic regression to control for potential confounders identified in bivariate analyses as well as variables of *a priori* clinical significance (gender, age, race/ethnicity). We will evaluate odds ratios with 95% confidence intervals to determine the relative magnitude of the adjusted association for each variable. Independent variables with strong correlations may result in collinearity. To address collinearity, we will construct separate models, each with one of the variables, and assess both the C statistic and the coefficients for the other variables in the model. Dropouts and missing data: We expect the majority of missing data to be due to dropouts due to moving or failure to remain in the study. We will investigate whether missing data is associated with patient characteristics. While data may not be missing completely at random, it may be reasonable to assume that data are missing at random. If this is the case, multiple imputations methods originally developed for sample survey data is applicable to clinical trials with dropouts and shown to be effective. Analytic software: We will use SAS version 9.4 (SAS Institute Inc, Cary, NC).

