# 1 Protocol Summary

Title:	Hospital-based Patient Navigation to Promote Smoking Cessation: a pilot RCT
Population:	Study population will include individuals (both men and women, all races and ethnicities) who meet inclusion criteria: (1) hospitalized smokers at BMC); (2) smoked at least 1 cigarette per day in the past month; (3) able to speak, read, and understand English; (4) able and willing to participate and provide informed consent; (5) has a primary care physician at Boston Medical Center; (6) at least 18 years of age; (7) must have plans to quit smoking; and (8) must have a working telephone.
	Sample size: 50
Intervention:	3 hours of patient navigation over the next 3 months
Objectives:	To assess effect of patient navigation to promote smoking cessation
Design/Methodology:	Enhanced Traditional Care : Participants randomized to this group will receive a resource card that has information on quitlines, BMC's outpatient program number, and websites for smoking cessation.
	Patient Navigation Intervention: We base our intervention on the
	Social Contextual Model, a multi-level approach to health education
	which stresses the influence of life experiences (e.g. stress and
	financial problems) and social relationships (e.g. social networks and family roles) on the practice of health behaviors.
	Intervention Components and Content. Participants will meet the
	navigator in person if she is available, or will be introduced by
	telephone. Participants will receive navigation from a trained
	navigator, based centrally in the Section of General Internal
	Medicine. Our navigator has a BA degree, and has extensive
	experience doing community health outreach. Participants will
	receive up to ten hours of patient navigation, in person or over the
	phone, over a 3-month period. We chose a ten-hour intervention dose based on 1) a prior study of motivational interviewing in low-income smokers and 2) our prior work studying patient navigation t promote smoking cessation. We have not designated a specific number of contacts, but allot a maximum of ten hours of patient
	navigation time per participant. The navigator will work flexible hours, contacting patients on evenings and weekends as necessary. Patient navigation contacts will involve individual counseling to help

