# 2 Background/Rationale & Purpose

Smoking cessation interventions are the 'gold standard' of healthcare cost effectiveness because they achieve more lifeyears gained for fewer resources than other interventions. Although there are several effective, guideline-recommended cessation treatments, low-income and minority populations suffer a disproportionate burden of tobacco-related morbidity and mortality due to high smoking rates, lack of access to cessation services, and lack of support for quitting. Hospitalization presents an opportunity to reach smokers who otherwise may not seek tobacco treatment. It offers a 'teachable moment' during which the risks of smoking are highlighted, leaving smokers more receptive to cessation interventions. Highly intensive counseling interventions that begin during the hospital stay and continue with supportive contacts for at least one month after discharge increase smoking cessation rates post-hospitalization by 40%, among patients hospitalized at non safety-net hospitals. However, we are unaware of interventions for hospitalized smokers that are effective among minority and low SES smokers hospitalized at safety-net hospitals. In a recent RCT (in press at JAMA Internal Medicine), we demonstrated that patient navigation and financial incentives substantially increased biochemically confirmed smoking cessation at 12 months among minority and low-SES primary care smokers. Patient navigation is a low-cost approach in which a community member trained in motivational interviewing (MI) assesses barriers to accessing evidence-based tobacco treatment, and addresses underlying social determinants of health. While the intervention improved quit rates in the ambulatory setting, we have not tested the efficacy of the patient navigation intervention component among recently hospitalized smokers. By implementing the intervention among recently hospitalized smokers (who may be more motivated to quit smoking), we will increase the proportion of participants that receive the minimum intervention dose from the navigator. We propose to pilot-test patient navigation among recently hospitalized smokers in preparation for a larger randomized trial. We propose the following specific aims:

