#### 8.3 Randomization

Randomization will occur after RA obtains informed consent from the participant. Participants will be randomly allocated in a 1:1 ratio to the intervention or comparator arm.

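### Section 11.3 uses a significance test to settle whether navigation raises 3-month cessation in a pilot sized only for feasibility, and plans no unadjusted between-arm difference with an interval.

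*Combined protocol and SAP*

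**What the plan says.** Section 11.3 gives the purpose of the comparison as "In order to determine if the patient navigation condition achieves greater smoking cessation at 3-month follow-up" and the method as "we will compare groups using chi- square tests and note differences that are statistically significant", at the 0.05 level and by intention to treat. No sidedness is stated; the chi-square test is non-directional.

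The same section promises percentages with 95% confidence intervals for engagement and self-reported cessation. It also plans a multiple logistic regression with odds ratios and 95% intervals, adjusted for gender, age, race/ethnicity and any confounders found in bivariate analyses. It does not mention an unadjusted between-arm difference or ratio with an interval.

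Section 11.2 plans on "randomizing fifty hospitalized smokers to one of 2 study arms", and Section 8.3 sets a 1:1 ratio, so there are 25 per arm. The stated grounds for that number are acceptability, feasibility and publishable results. Aim 2 (Sections 2 and 11.1) is acceptability and feasibility, whereas the Protocol Summary gives the objective as "To assess effect of patient navigation to promote smoking cessation". Self-reported cessation is a secondary outcome (Section 3.1). Section 2 says the pilot prepares for a larger randomised trial.

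**The concern.** The test is given an efficacy question that the sample was not chosen to answer. If power is very low at a realistic benefit, a real effect would usually be reported as no significant difference. On the rare occasions when it reached significance, the observed effect would be much larger than the true one. Neither statement helps the team planning the larger trial. An interval for the difference would, because it shows which effects the pilot leaves open. The plan stops short of that interval for the unadjusted comparison.

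**Working it through.** **Inputs from the documents**
- 50 randomised 1:1, so 25 per arm (Sections 11.2 and 8.3).
- Chi-square test at 0.05 (Section 11.3), taken as two-sided.
- Benchmark effect: Section 2 reports that intensive counselling continued after discharge can "increase smoking cessation rates post-hospitalization by 40%, among patients hospitalized at non safety-net hospitals".
- Retention (Section 4): at least 60%, stated for 1 month, which gives 0.60 × 25 = 15 per arm; and 70% in earlier 3-month assessments, which gives 0.70 × 25 = 17.5, taken as 18.

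**Assumptions**
- The 40% is relative (rate ratio 1.4).
- The control quit rate is 10%, 20% or 30%, with 5-50% as a wider range. The documents give no rate.

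**The plan's own figure.** There is none to reproduce: the number 50 has no power calculation behind it.

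**Power.** For a quitters in control and b with navigation, n per arm and pooled rate p̄ = (a + b)/(2n), the uncorrected chi-square test is significant when |z| > 1.96, where

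z = [(b − a)/n] / √[p̄(1 − p̄) × 2/n].

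Exact power is the sum of Bin(a; n, p) × Bin(b; n, 1.4p) over all significant tables, with p the control rate.

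| Control v navigation | 25 per arm | 18 per arm | 15 per arm |
|---|---|---|---|
| 10% v 14% | 7.4% | 5.3% | 4.2% |
| 20% v 28% | 10.7% | 8.1% | 8.4% |
| 30% v 42% | 15.6% | 12.6% | 10.6% |

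Over control rates from 5% to 50%, power with 25 per arm runs from 3.4% to 33.4%; with 15 per arm it runs from 1.0% to 19.5%. Fisher's exact test gives less: 2.2-9.2% with 25 per arm at control rates of 10-30%.

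For scale, by the normal approximation, 80% power at a rate ratio of 1.4 needs 1,035, 447 or 250 per arm at control rates of 10%, 20% or 30%. With 25 per arm and 20% in control, 80% power needs about 58% with navigation.

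**What a significant result would look like with 25 per arm.** The smallest favourable difference that can be significant is 0 v 4 quitters:
- p̄ = 4/50 = 0.08, and z = 0.16/√(0.08 × 0.92 × 0.08) = 2.09.
- 0 v 3 gives z = 0.12/√(0.06 × 0.94 × 0.08) = 1.79, which is not significant.

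The floor is therefore 16 points. The benchmark true differences are 4, 8 and 12 points. The mean observed difference among significant favourable results is 21.4, 28.6 and 32.7 points, which is 5.35, 3.6 and 2.7 times the truth. With 5/25 quitters in control, significance needs 12/25 with navigation, a gap of 28 points.

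**What an interval would show.** A result of 7/25 v 5/25 is +8 points, with a Newcombe 95% interval of −15.5 to +30.5 points. At a common rate p, the approximate half-width 1.96 × √[2p(1 − p)/25] is 17, 22 and 25 points at 10%, 20% and 30%.

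**The interval already planned.** Under the benchmark, the expected number of quitters among 50 is 25 × (0.10 + 0.14) = 6, 25 × (0.20 + 0.28) = 12 or 25 × (0.30 + 0.42) = 18. A logistic model with three prespecified covariates, plus others chosen from the data, is a fragile base for the only between-arm interval.

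**The case against.** Several points on the other side are sound.

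- The 40% belongs to another contrast and setting. In this trial both arms receive inpatient counselling (Section 4), and the hospital is a safety-net one. The figure is a benchmark, not this trial's design effect.
- The power figures depend on an assumed control rate. That power is low does not: it holds across the whole 5-50% range.
- The 15-per-arm column uses a minimum stated for 1 month, while the outcome is at 3 months. The plan is intention-to-treat with conditional multiple imputation, not a complete-case test. The 25- and 18-per-arm columns lead to the same conclusion.
- Cessation is secondary, and the section promises arm percentages with 95% intervals whatever the p-value. A reader could derive the difference from them.

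Three stronger readings are tempting, but the documents do not support them. A reader might infer that only significant differences will be reported; the first sentence of Section 11.3 sets no such condition. A reader might infer that the test is bound to misdirect the larger trial; no go/no-go rule uses it, and nothing says its result will size that trial. A reader might infer that chi-square results cannot be combined over imputations; methods for that exist, and the logistic coefficients pool directly by Rubin's rules.

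What stands against the plan is narrower. Cessation is the outcome for which Section 11.3 names a between-arm test; the stated purpose of that test is to answer an efficacy question; and the unadjusted contrast has no planned interval.

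**Conclusion.** The point holds as a mismatch between the purpose given to the test and what the sample can deliver. With a rate ratio of 1.4 as a benchmark and assumed control rates of 10-30%, power is about 7-16% with 25 analysed per arm, 5-13% with 18 and 4-11% with 15. It does not exceed about 33% at any control rate from 5% to 50%. If the true difference were 4-12 points, every significant favourable result with 25 per arm would overstate it, on average by roughly 2.7 to 5.4 times, and a non-significant result would carry little information. Either could mislead if taken as the answer on efficacy. The consequence is limited: the outcome is secondary, no decision rule depends on the test, and arm-level estimates are reported in any case. It is still worth correcting, because the change is small and improves what the pilot can pass on to the larger trial.

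**What to change.** In Section 11.3, replace the sentence that sets up the chi-square comparison with:

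*We will estimate the unadjusted between-arm difference in the proportion abstinent at 3 months, with a two-sided 95% CI (Newcombe or Miettinen-Nurminen when no imputation is used; if multiple imputation is used, the difference and its standard error pooled by Rubin's rules). This comparison is descriptive; no conclusion about efficacy will be drawn from statistical significance, and the interval, not the point estimate alone, will inform the larger trial.*

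The two cases are kept apart because standard Rubin pooling works on an estimate and its standard error and does not directly yield Newcombe or Miettinen-Nurminen intervals.

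Rewording the objective in the Protocol Summary as estimating the effect with its uncertainty is optional.

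The cost is a wording change in the SAP, with no extra participants, data or procedures. The report gives up a headline p-value.

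### The adjusted logistic model in section 11.3 carries too many, openly screened covariates for 50 patients, so a large true effect is overstated and scatters more; separately, it does not name the randomisation stratum

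*Combined protocol and SAP*

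**What the plan says.** Section 11.2 plans a pilot "randomizing fifty hospitalized smokers to one of 2 study arms". Section 8.3 sets the ratio at 1:1, so about 25 per arm.

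For 3-month cessation, section 11.3 states "we will compare groups using chi- square tests and note differences that are statistically significant at the" 0.05 level, and "Analyses will be based on intent-to-treat". It then adds a regression: "We will use multiple logistic regression to control for potential confounders identified in bivariate analyses", with gender, age and race/ethnicity included on clinical grounds. The output is "odds ratios with 95% confidence intervals to determine the relative magnitude of the adjusted association for each variable". For correlated covariates, "we will construct separate models, each with one of the variables, and assess both the C statistic and the coefficients" of the remaining variables.

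The section does not name the outcome of this model. It gives no candidate covariates, entry threshold or limit on their number, and no penalised or exact method. It does not say which of the separate collinearity models supplies the reported OR.

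Section 4 (Randomization Procedure) stratifies allocation by the patient's stated quit plan, with two levels. Section 11.3 names that factor in neither the test nor the model.

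**The concern.** An ordinary logistic fit with few events per coefficient is biased away from an OR of 1 when there is a true effect. Screening covariates on the same data adds terms and makes the result depend on which ones happen to pass. With 50 patients both problems are live.

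The adjusted OR is meant to be reported with its interval, section 11.2 wants publishable results ("We believe an n of 50 is the necessary sample size to determine acceptability and feasibility, and to have publishable results"), and section 2 presents the pilot as preparation for a larger trial. At stake is the quality of a published effect estimate.

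The missing stratum is a separate matter of consistency: a factor used to allocate patients would normally appear in the adjusted analysis.

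**Working it through.** **No plan figure to reproduce.** Section 11.2 gives 50 without a control rate, effect size or power. The rates and effects below are assumptions.

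**Information per coefficient.** With 25 per arm, control rate p0 and odds ratio OR, p1 = OR·p0/(1−p0) ÷ [1 + OR·p0/(1−p0)]. The limiting count is the smaller of events and non-events. The model has about 6 terms: arm, gender, age, two for race/ethnicity (three groups assumed) and about one screened covariate.

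- p0 = 20%, OR 3: p1 = 0.75/1.75 = 42.9%. Events = 5 + 10.7 = 15.7, and 15.7/6 = 2.6 per term.
- p0 = 40%, OR 3: p1 = 2/3. Events = 10 + 16.7 = 26.7, non-events = 23.3, and 23.3/6 = 3.9 per term.
- p0 = 20%, OR 1: 10 events, and 10/6 = 1.7 per term.

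**Simulation.** There were 6,000 trials per setting, with N = 50 and all outcomes known. The two strata were equal, with 1:1 allocation balanced within them (blocks of 4, an assumption) and a stratum OR of 2. Race had three levels (50/30/20%). There were 5 or 10 candidates including the stratum, screened on outcome at p<0.10, and no other covariate had an effect. The Firth model contains arm, stratum, gender, age and race. True OR 3:

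| Model | Median, 20% rate | Median, 40% rate | IQR, 20% rate | OR above 6, 20% rate |
|---|---|---|---|---|
| As planned | 3.6-3.7 | 3.6 | 2.1-7.0 | 29-30% |
| Arm + stratum, ordinary fit | 3.2 | 3.2 | 2.0-5.2 | 20% |
| Firth | 2.9 | 3.0 | 1.9-4.7 | 16% |

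Allowing for repeat runs and both rates, the medians are about 3.5-3.7, 3.2 and 2.9-3.1. The shares above 6 (twice the truth) are 25-30%, 17-20% and 14-16%. At a true OR of 2 the medians are about 2.2-2.3, 2.1 and 2.0. At a true OR of 1 all are about 1.0.

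**Different assumptions.** A second simulation used a stratum log-OR of 1 and screening at p<0.20 (20% rate, true OR 3). The planned model had median 3.55 and SD of the log OR 1.08; for arm + stratum and for Firth with fixed covariates the SD was 0.72. With stratum and fixed covariates non-prognostic, the planned model's geometric mean was still 4.12. The excess is therefore a small-sample effect, not only non-collapsibility.

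**Which part of the plan causes it (20% rate, true OR 3).** Gender, age and race with no screening give 3.4, and adding the stratum to that ordinary fit gives 3.6. In the second simulation (geometric means) the same step goes from 3.44 to 3.88, and in the screened model from 4.06 to 4.68. Treatment alone gives 2.83, and treatment + stratum 3.04. So leaving the stratum out lowers the OR, and deleting the screen alone does not cure the problem.

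**Sensitivity (20% rate, true OR 3, first set of assumptions).** The planned median runs from 3.5 (two race groups, 5 candidates) to 4.1 (screening on outcome or arm). Section 4 cites 70% retention at 3 months in earlier work, and 50 × 0.70 = 35. With 35 complete cases the planned model gives 3.9-4.7; multiple imputation of all 50 gives 3.9-4.5; Firth at 35 gives 2.8-3.0.

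**Coverage.** At 20-40% control rates the planned model's 95% Wald interval covers at about 94-96% among estimable fits. Firth profile-likelihood intervals cover at 94.5-96.0% for OR 3.

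**The case against.** The other side has four good points.

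- The logistic model is supportive. Section 11.3 judges cessation by chi-square, and Aim 2 concerns acceptability and feasibility. This stands and limits the severity.
- The 95% Wald interval remains about right at these rates, so the published interval would show how imprecise the estimate is. This stands too. What remains is a displaced point estimate with wider scatter than the same data need give.
- The sizes rest on assumed rates, candidates and thresholds. That is true. The direction held across the settings tried for the screened model, but it is not universal: with a very strong stratum (log-OR 2), the fixed-covariate model without the stratum gave 2.91 for a true 3, while the screened model gave 3.37.
- A stratified test brings no dependable gain. With balanced allocation, Cochran-Mantel-Haenszel (CMH) power was 72% v 74% for chi-square with strata at 5/15%, 64% v 65% at 10/30%, 60% v 62% at 20/40% and 66% v 63% at 10/50%. This stands, so that test is only optional.

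A reader might infer three stronger things. One is that omitting the stratum causes the exaggeration; the calculation shows the reverse. Another is that the omission inflates type I error; it does not, and the chi-square is conservative only if allocation is balanced within strata and the stratum is strongly prognostic. The third is that this OR will size the next trial. Section 2 speaks only of preparing for one, and no section assigns the OR that use.

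**Conclusion.** The concern holds, at minor to moderate severity. If navigation has a large effect (true OR 3) and the control quit rate is 20-40%, the planned adjusted OR would typically read 17-23% too high (3.5/3 to 3.7/3), against about 7% for arm + stratum (3.2/3), and would more often exceed twice the truth. At a true OR of 2 the excess is about 10-15% (2.2/2 to 2.3/2). Under no effect there is no bias. These sizes depend on the assumptions listed, since the documents give no quit rate, candidate list or screening rule.

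The absence of the quit-plan factor is a separate departure from the stratified design, and it pulls the OR toward 1. It matters only if two strata really exist. Section 4's inclusion text prints one eligible response, its randomisation text uses two, and sections 6.1 and 8.1 admit patients on a broader quit intention. If only one response is eligible, this part falls away and the model part remains.

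**What to change.** Before using the stratum, reconcile section 4's one-response inclusion text with its two-level stratification sentence and with sections 6.1 and 8.1. Then, in section 11.3:

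1. Delete covariate selection by bivariate analyses and the separate collinearity models.
2. Prespecify one model, labelled supportive, for 3-month cessation: arm, quit-plan stratum, gender, age and race/ethnicity, with categories fixed in advance. Fit it by Firth-penalised logistic regression with profile-likelihood 95% intervals. If penalised fitting is not wanted, use arm + stratum by ordinary logistic regression. Do not simply add the stratum to the ordinary full model.
3. Optionally, add a CMH test stratified by quit plan, for consistency with the design and with no claim of extra power.

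If only one quit-plan response is eligible, drop the stratum throughout and keep the rest.

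The cost is a few lines, with no extra patients or data and no change to randomisation; the methods are available in the SAS release the plan names. There would be fewer exploratory covariate odds ratios, and Firth reads slightly low when events are few (2.8 for a true 3 at a 10% control rate). Power for OR 3 at a 20% rate is about the same as for the planned model's Wald test (36-37% v 37%).

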## 3 Objectives

#### 3.1 Study Outcome Measures

Primary Outcome: whether a prescription for an FDA-approved smoking cessation medication was sent to the participants' pharmacy (Y/N, based on chart review)

Secondary outcomes: Self-reported smoking cessation at 3 months, utilization of smoking cessation medication, stage of change assessed at baseline and 3 months, according to the following categories: pre-contemplation, contemplation, preparation, or action. For each participant, we compare stage of change at baseline vs. 3 months. We will also measure

level of nicotine dependence (baseline and 3 months), measured by the Fagerstrom Test for Nicotine Dependence, and use of other tobacco treatment support (3 months), defined as self-report of all tobacco treatment support received, including support from non-study sources, including the internet, during the 3-month study period.

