Retention: We expect to retain at least 60% of participants from baseline to 1-month follow-up, based on our prior experience conducting assessments at 3 (70% retention) and 6 months (76% retention) in similar populations. To maximize retention we will collect contact information including home address, phone, cell phone, beeper, e-mail, and phone numbers of three contacts. We will provide \$20 for completion of the 1-month assessment.

Patient Navigation Intervention: We base our intervention on the Social Contextual Model, a multi-level approach to health education which stresses the influence of life experiences (e.g. stress and financial problems) and social relationships (e.g. social networks and family roles) on the practice of health behaviors.

Participants will meet the navigator in person if she is available, or will be introduced by telephone. Participants will receive navigation from a trained navigator, based centrally in the Section of General Internal Medicine. The navigator has a BA degree, has extensive experience doing community health outreach, and has previously completed the University of Massachusetts "Basic Skills for Working with Smokers Online Course." Participants will receive up to ten hours of patient navigation, in person or over the phone, over a one-month period. We chose a two-hour intervention dose based on 1) a prior study of MI in low-income smokers and 2) our prior work studying navigation to promote smoking cessation. We have not designated a specific number of contacts, but allot a maximum of ten hours of patient navigation time per participant. The navigator will work flexible hours, contacting patients on evenings and weekends as necessary. Patient navigation contacts will involve individual counseling to help the patient achieve abstinence. We will adapt and incorporate into the PN script a modified version of the WE CARE Survey, which consists of 12 questions designed to: (1) identify six unmet material needs (inadequate education, employment, food security, housing, childcare, and household heat) by self-report (e.g., Are you employed?) and 2) determine whether participants would like assistance with each problem (e.g., If No, do you want help?). The survey takes less than five minutes to complete and has a test-retest reliability of 0.92.7 Thus, navigators will screen participants for social determinants of health which

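### Missing 3-month self-reported cessation is handled, at most, under a missing-at-random assumption that the planned check cannot test, and no planned analysis would show how far the arm comparison depends on it

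*Combined protocol and SAP*

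**What the plan says.** Section 3.1 lists "Self-reported smoking cessation at 3 months" as a secondary outcome. The primary outcome, whether a cessation prescription was sent to the pharmacy, is recorded as "Y/N, based on chart review". Section 4 has the 3-month data collected by phone.

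Section 11.3 compares cessation at 3 months between arms by chi-square test at the 0.05 level and names no between-arm test for any other outcome. It states intent-to-treat but gives no rule for a participant whose outcome is missing. On missing data it says: "We will investigate whether missing data is associated with patient characteristics". It concedes that data may not be missing completely at random, adds that "it may be reasonable to assume that data are missing at random", and says that multiple imputation is applicable if so. It gives no imputation model, no alternative if the assumption is rejected, no analysis under another assumption, and no report of retention by arm.

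On the amount of missing data, Section 4 says "We expect to retain at least 60% of participants from baseline to 1-month follow-up", citing prior experience with "assessments at 3 (70% retention) and 6 months (76% retention) in similar populations".

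**The concern.** Neither result of the planned check tells the analyst what is needed. An association between missingness and baseline characteristics is compatible with missing at random. No association is compatible with missingness driven by smoking status at follow-up, because that status is unobserved in exactly the people concerned. Yet this check is the only step offered to decide whether imputation is used.

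Participants enrol with a plan to quit and are later phoned to ask whether they smoke, so it is credible that answering depends on the answer. Retention may also differ by arm: Section 7.2 gives the navigation arm continuing personal contact, while Section 7.1 gives the comparator a resource card.

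The stake is the cessation comparison. It is secondary, but it is the one the plan tests, and Section 2 presents the pilot as preparation for a larger randomized trial. A distorted estimate could carry into that design.

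**Working it through.** The plan states no quit rates, effect size or power, so there is no figure of its own to reproduce.

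**Inputs from the documents**
- Sample: "randomizing fifty hospitalized smokers to one of 2 study arms" (Section 11.2), allocated 1:1 (Section 8.3), so 25 per arm.
- Retention (Section 4): at least 60% at 1 month for this trial; 70% at 3 months and 76% at 6 months in prior work.

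**How many outcomes could be missing**

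Missing = 50 × (1 − retention). With nothing assumed about the missing, the bounds on the arm difference are 2 × (1 − retention) wide.

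| Retention | Missing of 50 | Width of bounds on the arm difference |
|---|---|---|
| 60% | 20 | 80 points |
| 70% | 15 | 60 points |
| 76% | 12 | 48 points |

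**What selective response does**

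Let p be the true quit rate, rq the response rate of quitters and rs that of smokers. All three are assumptions here; the documents give none of them.
- Responder quit rate = p·rq / (p·rq + (1 − p)·rs)
- Missing = smoking rate = p·rq

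*Case A: no true effect, smokers respond differently by arm.* p = 0.20 and rq = 0.85 in both arms; rs = 0.75 with navigation and 0.50 without.
- Navigation: 0.17 / (0.17 + 0.60) = 0.17/0.77 = 22.1%
- Comparator: 0.17 / (0.17 + 0.40) = 0.17/0.57 = 29.8%
- Difference −7.7 points. Average retention (77% + 57%)/2 = 67%, inside the range above.
- Missing = smoking: 17% v 17%, difference 0.
- Swapping the two smoker response rates reverses the sign to +7.7.

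*Case B: no true effect, quitters respond differently by arm.* p = 0.20. In the comparator everyone responds at 70%. With navigation, overall response is also 70%, but quitters respond at 90%.
- Responders: 0.18/0.70 = 25.7% v 0.14/0.70 = 20.0%, difference +5.7 points.
- Missing = smoking: 18% v 14%, difference +4 points.
- So missing = smoking does not always remove the artefact either.

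*Case C: true 20% v 10%, the same selection in both arms* (rq = 0.85, rs = 0.60).
- Responders: 0.17/0.65 = 26.2% v 0.085/0.625 = 13.6%, difference 12.6 points against a true 10.
- Missing = smoking: 17% v 8.5%, difference 8.5 points.
- Responder odds ratio: (0.17/0.48)/(0.085/0.54) = 2.25, equal to the true odds ratio, 0.25/0.111 = 2.25.

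The responder rates are crude. Multiple imputation would be close to them if its covariates add little information about cessation.

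**What it can do to the planned test**

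With invented counts at 60% retention (15 observed per arm), 7/15 v 2/15 gives an uncorrected chi-square p = 0.046. The same data with missing = smoking, 7/25 v 2/25, give p = 0.066. Assigning the missing to either extreme moves the difference from 7/25 − 12/25 = −20 points to 17/25 − 2/25 = +60 points.

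**The case against.** The case for leaving the plan alone has several sound parts.

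- **Weight.** Cessation is secondary, the stated aim is acceptability and feasibility, and the primary outcome comes from the chart. This stands. A reader might infer that the trial's main result is at risk; the documents do not support that.
- **Amount of dropout.** A reader might take 30% to 40% as the expected loss. The 60% is a floor, and it is for 1 month. The plan states no 3-month expectation for this trial, its text moves between 1-month and 3-month follow-up, and prior work reached 76%. The fair range is 12 to 20 of 50.
- **Direction.** A reader might infer that navigation will look better than it is. Case A gives a false deficit and Case B a false gain, so only distortion in either direction can be claimed. Where selection is the same in both arms, the odds ratio is not biased at all (Case C).
- **Commitment.** A reader might say that the plan firmly rests on missing at random. The wording is conditional and commits to no method. That leaves the gap open, because the test could fall back on completers.
- **Reason for dropout.** Section 11.3 expects losses from moving or from not staying in the study, and no passage names relapse. Dependence on smoking status is a possibility to allow for, not an established fact.
- **Noise.** In Case A about 19 and 14 people respond (25 × 0.77 and 25 × 0.57), and the 95% half-width for the difference is about 1.96 × √(0.221 × 0.779/19.25 + 0.298 × 0.702/14.25) = 30 points. A bias of 8 points is small beside that. But the confidence interval does not reflect the bias, and a larger trial with the same missing-data plan would not remove it.

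**Conclusion.** The point holds as a moderate one that is worth correcting. The planned check cannot support the assumption on which the imputation depends, and with about 12 to 20 of 50 outcomes possibly missing, no planned analysis would reveal how far the cessation comparison depends on it. Under assumed response rates with no true effect, the false difference is about 6 to 8 points, with either sign. The size rests wholly on those rates and on imputation covariates adding little; the inability of the check to test the assumption does not.

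A reader might go further and conclude that missing = smoking is the correct rule. Case B shows why not: it carries its own bias when quitters respond differently by arm. The case is for showing the result under more than one assumption.

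**What to change.** In Section 11.3:

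1. Remove the wording that makes imputation conditional on the missingness check. Keep the check as description.
2. Keep multiple imputation, with arm and a small set of baseline predictors, for example the randomization stratum and the baseline dependence score. The model must be small: Cases C and A imply only about 6 to 9 observed quitters (25 × 0.17 + 25 × 0.085 = 6.4; 2 × 25 × 0.17 = 8.5).
3. Pre-specify a missing = smoking analysis.
4. Pre-specify a simple by-arm tipping-point analysis: let the number of quitters among the missing run from none to all in each arm, and show where the direction of the difference changes.
5. Report retention by arm.
6. Report cessation under each assumption and state whether its direction changes. A rule that bars any statement of effect unless direction holds across the whole range would be too strict for a pilot of 50.

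The cost is a few sentences and a little extra analysis, with no new data. The result becomes a range and may look less favourable.
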